2.0 STUDY OBJECTIVES

Aim 1:

Complete refinements to the FamCHESS-C app.

Aim 2:

Conduct a balanced RCT to test the following outcomes: Primary: 1) drinker % heavy drinking days, 2) dyad quality of life. Secondary: 3) dyad relationship satisfaction, 4) dyad psychological/physical conflict, 5) drinker no heavy drinking days, 6) drinker % days alcohol/drug use, 7) dyad COVID vaccination rates, 8) drinker alcohol- and drug-related problems. Exploratory: 9) partner % days alcohol/drug use, 10) dyad crisis healthcare use, 11) dyad technology satisfaction. We hypothesize that outcomes will be more favorable in FamCHESS-C relative to ACHESS-C, and both will be more favorable relative to smartphone control.

Aim 3:

Examine mediation effects of dyad's competence, relatedness, and motivation; drinker's interim change in % days of alcohol and drug use, and extent of app use for comparisons of ACHESS-C and FamCHESS-C. Examine moderation of effects of condition by drinker sex, severity of drinker's baseline alcohol use, drinker engagement in treatment for AUD/SUD, and dyad's baseline relationship satisfaction.

Aim 4:

Conduct a small-scale (20 dyads) formative evaluation using an implementation science model to collect qualitative data on perceptions of difficulties and benefits of ACHESS-C and FamCHESS-C use. In preparation for this R01 submission we have been conducting an NIH- funded R34 study, testing the use of a partner-focused CHESS app and feel that the data from that research study, has fulfilled the needs of Aim 4.

Study Coordination

The UW-Madison Center for Health Enhancement Systems Studies (CHESS) is the coordinating site for this study. The UW study coordinator will oversee all activities at the recruitment site which includes:

- developing site specific recruitment and data collection processes that meet study objectives;
- training site staff on protocol procedures prior to start of recruitment and continuous monitoring to assure compliance with the protocol and human subjects regulation;

- communicating with site staff via weekly conference calls to monitor progress, inform of protocol changes/distribute new version of protocol, and address unanticipated issues or challenges;
- and manage all study data.

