Study design and outcomes. We will conduct a 24-month randomized trial (*N*=198 dyads, 66 in each arm, to yield approximately 180 dyads at 8-month analysis) in which assessment and intervention will all occur remotely. Dyads comprising one person who drinks at risky levels or has AUD (any severity) and one family partner (any family member) will be recruited and randomly assigned to 8 months of either: 1) smartphone control (both drinker and partner receive smartphones with numbers for AA, NA, Al-Anon, ACOA and crisis hot lines); 2) ACHESS-C (drinker receives a phone with ACHESS-C; partner receives a phone with numbers for Al-Anon, ACOA, and crisis hot lines); or 3) FamCHESS-C (drinker and partner receive a phone with FamCHESS-C). In all conditions, both members of the dyad complete baseline assessment plus follow up assessments at 4, 8, and 12 months (i.e. 8-month active app/phone use phase plus follow-up 4 months later).

[figure not shown]
Primary outcomes: 1) drinker % heavy drinking days, 2) dyad quality of life.

Secondary outcomes: 3) dyad relationship satisfaction, 4) dyad psychological/physical conflict, 5) drinker no heavy drinking days, 6) drinker % days alcohol/drug use, 7) dyad COVID vaccination rates, 8) drinker alcohol- and drug-related problems.

Exploratory outcomes: 9) partner % days alcohol/drug use, 10) dyad crisis healthcare use (ER, 30-day hospital readmits), 11) dyad satisfaction with technology.

Rationale for our primary outcomes: Quality of life captures the physical and socioemotional impacts of COVID and alcohol and comorbid drug use for drinkers and partners. Reductions in alcohol and comorbid drug use are the primary means by which we hope to improve quality of life.

Hypothesis 1: Outcomes will be more favorable in FamCHESS-C relative to ACHESS-C, and both will be more favorable relative to smartphone control.

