competence, relatedness, and motivation for both drinker and partner, together with interim reductions in the drinker's % days with use of alcohol and drugs, will mediate effects of condition on other improvements in outcomes. For comparisons of ACHESS-C vs. FamCHESS-C, we will also test use of the app as a mediator. Further, we will examine moderation of effects of condition by drinker sex, severity of drinker's baseline alcohol use, drinker engagement in treatment for AUD/SUD, and dyad's baseline relationship satisfaction. Details of measures for all variables in the figure are in the Measures section below.

AIM 4: Conduct a Formative Evaluation Using an Implementation Science Model. Using our Organizational Change Model (OCM),⁷⁵ we will collect qualitative data from 20 drinkers and 20 family partners in the RCT on perceptions of difficulties and benefits of ACHESS-C and FamCHESS-C use. In preparation for this R01 submission we have been conducting an R34 testing the use of a partner-focused CHESS app and feel that the data from that research study, has fulfilled the needs of Aim 4.

Privacy and Confidentiality:

To mitigate the risk of patient breaches of confidentiality, all subjects will be assigned a code number. A list of subject code numbers will be maintained by the UW project director and stored in a password protected spreadsheet. Participant surveys will be identified by code number only. The UW study coordinators will assist patient subjects in choosing codenames and passwords to use to login to the A-CHESS-C or FamCHESS-C system. Patients will be instructed not to use their real names as a codename and will be made aware of the potential dangers of divulging confidential information (e.g. real names or telephone numbers).

Prior to gaining access to our data, all students, faculty and staff must provide our Data Security Officer a copy of their certificates of completion of the UW Madison Human Subjects online training and the online HIPAA Privacy Rule training. Furthermore, they are required to complete training on Center security procedures and policies and sign a Center Data Security Policy Certification upon completion of this training.

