6.0 MEASUREMENT OF EFFECT

Variables reflect the conceptual model (see Figure 3, above) and study aims. Measures chosen have good psychometric properties with similar populations. Where possible, we used PhenX and PROMIS measures (e.g. PROMIS 29.2) so that results are comparable to other studies.⁸⁵ Our primary outcome is percent days of heavy drinking, but given 2015 FDA draft guidelines we also include number of patients with *no* heavy drinking days per period as a secondary outcome.⁸⁶ Table 2 lists our measures, number of questions, and sources, with references to validation studies where relevant. In the R34, we collected much of the same data we propose to collect in the RCT. Survey completion time averaged about 90 minutes.

Table 2: Proposed Measures, Scales, and Sources for Study Outcomes and Other	
Variables	

MEASURE	WHO	SOURCE	REFERENCE	# QUEST	TIME (MONTH)
		Primary Outcomes			
% days heavy drinking	Drinker	Timeline Follow Back ⁸⁷	Johnston et al. ⁸⁸	7	0, 4 , 8, 12
Quality of life	Dyad	PROMIS 29.2	Hamilton et al.85	29	0, 4, 8, 12
		Secondary Outcomes			
Relationship satisfaction	Dyad	OQ-45.2 ⁸⁹	Beckstead et al.89	45	0, 4 , 8, 12
Physical/psychological conflict	Dyad	Rev. Conflict Tactics	Straus et al.90	20	0, 4 , 8, 12
No heavy drinking days	Drinker	Timeline Follow Back ⁸⁷	Johnston et al. ⁸⁸	7	0, 4 , 8, 12
% days alcohol or drug use	Drinker	Timeline Follow Back ⁸⁷	Johnston et al. ⁸⁸	7	12
COVID vaccination completion	Dyad			1	0, 4 , 8, 12
Drinking/drug problems	Drinker	Clinical evaluation guide	Spitzer et al.91	5	0, 4 , 8, 12
	Ē	Exploratory outcomes			
Crisis healthcare use (ER, 30 day readmits)	Dyad	Treatment Services Reviews	McCollister & French ⁹²	3	0, 4 , 8, 12
% days alcohol or drug use	Partner	TLFB last 60 day	Collins et al. ⁸⁷	11	0, 4 , 8, 12
Satisfaction with technology	Dyad	Tech Accept Model93	Szajna ⁹⁴	26	4, 8, 12
		Mediators			
Competence	Dyad	CCQ / # of skills used	Schroder & Ollis ⁹⁵	11	0, 4 , 8, 12
Relatedness	Dyad	Revised Important People	Zwiak et al.96	14	0, 4 , 8, 12
Motivation	Dyad	Brief Self Control Scale	Tangney et al.97	13	0, 4 , 8, 12
Reductions over 8 months % days alcohol or drug use	Drinker	Timeline Follow Back ⁸⁷	Johnston et al. ⁸⁸	7	0, 4 , 8
For ACHESS-C vs. FamCHESS-C: use of app	Dyad	Smartphone data	N/A	0	0, 4 , 8, 12
		Moderators			
Sex	Drinker			1	0
Concurrent treatment services	Drinker	TSR	McLellan et al.98	10	0, 4 , 8, 12
Severity baseline alcohol	Drinker	Smartphone data	N/A	0	0, 4 , 8, 12

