8.0 STATISTICAL CONSIDERATIONS

Data Analysis Plan. The analysis will: 1) explore differences among the three arms over the 8-month active intervention phase and then the 4-month follow-up phase of the RCT; 2) explore the conceptual model (see Figure 3) that considers the relations between the primary and secondary outcomes, and drinker and partner mediators, moderators, and covariates; and 3) examine how the dyad's demographic characteristics (e.g. young drinker and older partner) affect intensity and length of ACHESS-C and FamCHESS-C use and SDT mediators of relatedness, motivation, and competence on study outcomes.

Assumptions and randomization effect. We will report descriptive statistics for all demographic and clinical variables in both arms to ensure that randomization produced comparable groups; if not, variables with significant differences will be included as covariates in a sensitivity analysis. Sensitivity analyses (with and without covariate adjustment) will determine the robustness of covariate-related error control. All outcome variables will be examined using standard summary statistics, visualizations, and tests for normality and homoscedasticity. Data will be transformed for continuous outcomes that do not meet the assumptions of a normally distributed outcome.

Effects of study arm on primary and secondary outcomes (Aim 2). Linear mixed effects models (LMEM)—which account for dependence among successive observations on the same drinker and can address incomplete data—will be used to examine effects of study arm (FamCHESS-C vs. ACHESS-C vs. control, a between-subjects factor) on drinker outcomes over time. We will conduct specific treatment X time contrasts both between and within groups to test time-based effects. For binary, count, and other non-normal data, generalized linear mixed effects models will be used.

Mediation of effects of study arm on primary outcomes (Aim 3). Structural equation modeling (SEM) will explore the effects of mediation on the relation between study arms and our two primary outcomes. We anticipate that the impact of study arm on drinker heavy drinking days and dyad quality of life will be mediated by SDT (competence, relatedness, and motivation) and by drinker's interim change in percent alcohol and drug use days. SEMs involving app use will be run separately for only the ACHESS-C and FamCHESS-C arms.

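### Aim 3 tests change in alcohol/drug-use days as a mediator of heavy drinking days, which are part of them, without fixing the lag or adjusting for earlier heavy drinking

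*Combined protocol and SAP*

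**What the plan says.** Section 8.0 (mediation, Aim 3) plans structural equation models for the two primary outcomes. It expects that the "impact of study arm on drinker heavy drinking days and dyad quality of life will be mediated by SDT" constructs and also by the drinker's "interim change in percent alcohol and drug use days". Heavy drinking days are therefore named as an outcome of this mediator.

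The other statements of Aim 3 differ in scope:

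- Section 2.0 lists "interim change in % days of alcohol and drug use" as a mediator and does not say for which outcomes.
- The Aim 3 paragraph in section 5.0 says the mediators "will mediate effects of condition on other improvements in outcomes", which may exclude drinking itself.
- The rationale for the primary outcomes in section 5.0 ties use to quality of life: "Reductions in alcohol and comorbid drug use are the primary means by which we hope to improve quality of life".

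In Table 2 (section 6.0) the mediator row is "Reductions over 8 months % days alcohol or drug use", from the drinker's Timeline Follow Back at months 0, 4 and 8. The primary outcome row, percent "days heavy drinking", has the same respondent and instrument, at months 0, 4, 8 and 12. Neither row states a look-back window. The only stated window is in the partner's row ("TLFB last 60 day").

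**The concern.** A heavy drinking day is a day on which alcohol was used, so it is counted in both variables. When a heavy day turns into a day without use, the mediator falls by definition. A model with arm, use days and heavy days from the same window will then assign part of the arm effect to use days, even if a change in use days causes nothing.

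An earlier mediator does not settle the matter. Heavy drinking persists from one interview to the next, and two change scores can share a baseline. Use days at month 4 therefore predict heavy days at month 8, partly because they contain heavy days at month 4.

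At stake is a conclusion about mechanism: that the apps reduce heavy drinking by reducing days of use. The plan as written could report this when it is not so.

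**Working it through.** The plan gives no figure for the mediation analysis, so there is none to reproduce.

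**Inputs from the documents.** About 180 dyads at month 8 (sections 5.0 and 7.0), so 180/3 = 60 per arm. Section 8.0 (Power) gives d=.40 for adjacent arms and d=.80 for FamCHESS-C vs. control. The introduction says the apps serve people who are cutting down as well as those who stop, so f between 0 and 1 is plausible.

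**Assumptions.** The documents give no variances or correlations. I take r from 0.25 to 4, autocorrelation between interviews of 0.3 to 0.7, and two-sided 0.05 tests. Use days have no causal role.

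**Model.** Heavy days H = −d·arm + eH. Other use days L = (1−f)·d·arm + eL, with var(eL) = r·var(eH) and the errors independent. Mediator U = H + L.

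**Shared window.**

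- Arm to mediator: a = −d + (1−f)d = −f·d.
- Mediator to outcome given arm: b = var(eH)/[var(eH)+var(eL)] = 1/(1+r).
- Total effect: −d. Apparent mediated share: ab/(−d) = f/(1+r).

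At f=1, with the share of simulated trials in which both paths are significant (ranges are repeat simulations):

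| r | share | d=.40 | d=.80 |
|---|---|---|---|
| 0.25 | 80% | 48–50% | 97–98% |
| 0.5 | 67% | 42% | 94% |
| 1 | 50% | 33–35% | 87–88% |
| 2 | 33% | 24% | 69–72% |
| 4 | 20% | 16–17% | 49–51% |

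At f=0.5 the shares halve to 40–10%. Over r = 0.25–2, false significance is then 16–9% at d=.40 and 49–24% at d=.80. At f=0 the share is 0% and false significance about 5%.

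**Change from month 0 to 8, outcome at month 8.** The share is f/(1+r) for a change-score outcome and f/[2(1+r)] for the unadjusted month-8 level.

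**Month-4 use days, outcome at month 8, no adjustment.** At f=1 the share is autocorrelation/(1+r). With r=1 that is 0.3/2 = 15%, 0.5/2 = 25% and 0.7/2 = 35%. At d=.80 both paths are significant in 57%, 86% and 87% of trials. Adding month-4 heavy days to the outcome model brings the share to about 0% and significance to about 5%.

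**Change from month 0 to 8, outcome at month 12, f=1.**

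- Low end: unadjusted month-12 level, equal correlation ρ between all interviews. Covariance of the heavy-day change with the outcome is ρ − ρ = 0, so the share is 0%.
- High end: change-score outcome, correlation 0.7 per four-month step (0.49 over two, 0.343 over three), r=0.25. Covariance = 0.7 − 0.343 − 0.49 + 1 = 0.867. Variance of the heavy-day change = 2(1−0.49) = 1.02. Share = (0.867/1.02)/1.25 = 68%.
- Adjusting for heavy days at months 0 and 8 gives a mediator coefficient of 0 and joint significance of 3–6%. Once both heavy-day values are held fixed, only the change in other use days is left in the mediator, and in this model it is unrelated to later heavy days.

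**Bounded check.** Days were limited to a 60-day window (borrowed from the partner's row), with heavy days cut by 30% (implied d 0.38–0.62). The same-window share is 20–53% at f=1 and 12–28% at f=0.5, falsely significant in 39–95% and 16–46% of trials. At f=0 false significance is 5%.

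**The case against.** The strongest reply is that the plan already implies a time order. It calls the change *interim*, and the mediator row stops at month 8 while the outcome runs to month 12. Table 2 also shows drinker use days as a secondary outcome at month 12 only, although that cell may be a PDF artefact. The Aim 3 paragraph in section 5.0 speaks of other improvements, which points away from drinking mediating drinking. Figure 3 is not shown and that paragraph's opening is missing, so an ordering may be stated there. The analysis is also described as exploring mediation.

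Much of this stands. The wordings need reconciling but do not flatly contradict each other, and an earlier mediator may well be intended. But section 8.0 names heavy drinking days, and no visible text fixes the lag, the outcome month or adjustment for earlier heavy days. The calculations show that a lag without that adjustment is not enough.

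The reply is also right about size. The ranges are wide and rest on assumed inputs, and the artefact vanishes if every avoided heavy day becomes a lighter use day.

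**Conclusion.** The concern holds for one path: use days to heavy drinking days. In a shared window, overlap produces an apparent mediated share of f/(1+r). At f=1, both paths are falsely significant in about 49–16% of trials at d=.40 and 97–49% at d=.80 for r = 0.25–4. With a later outcome the share depends on choices the plan leaves open. That the mediator contains the outcome needs no assumption; every percentage does.

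A reader might infer three stronger points that the documents do not support:

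- *Overlap alone explains any mediation found.* That fits only shared windows. With separate windows the remaining artefact comes from persistence of heavy drinking and a shared baseline, and it can be zero.
- *The path has to be deleted.* A lag with adjustment for earlier heavy days removes the false coefficient in the simulated model.
- *Aim 3 as a whole, or the trial's main result, is compromised.* The Aim 2 arm comparisons, the quality-of-life mediation and the competence, relatedness and motivation paths do not have this overlap.

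**What to change.** In section 8.0, limit the use-days mediator to dyad quality of life, in line with the Aim 3 paragraph of section 5.0, and align the Aim 3 wording in sections 2.0, 5.0 and 8.0.

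If the path to heavy drinking days is kept, state two things:

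- The mediator window ends before the outcome window: for example, change from month 0 to 4 with the month-8 outcome, or from month 0 to 8 with the month-12 outcome. State the drinker's look-back window too, so that this can be checked.
- The model adjusts for heavy drinking days at baseline and at the mediator month.

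Leave the quality-of-life and competence, relatedness and motivation paths as planned.

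Replacing the mediator with non-heavy use days is not a safe shortcut, because days sum to a fixed total. In the bounded check that version was falsely significant in 5% of trials at f=1, 16–53% at f=0.5 and 37–97% at f=0.

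The cost is wording only, since all the months are already collected. One exploratory path is dropped, or is estimated less precisely after adjustment.

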7.0 STUDY PARAMETERS

198 dyads will be recruited, 66 in each of 3 conditions to yield approximately 180 dyads at 8-month analysis.

They will be allowed to keep the phone, so that they could continue to use those interventions if they had other ways to access the two systems. Partners in the A-CHESS group will not have access to either app.

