Qualitative Analyses (Aim 4). Transcripts of qualitative interviews concerning perceived difficulties and benefits of app use will be examined using Braun and Clarke's¹⁰² six-phase procedure for thematic analysis: 1) familiarization with data, 2) generation of initial codes, 3) identifying instances of themes, 4) review of themes, 5) defining and naming themes, 6) production of findings. To improve consistency and accuracy, coders will work separately using NVivo software; findings will be compared and discussed until consensus is reached.

Interim Analyses and Stopping Plan. The interim analyses are solely to check whether the stopping plan needs to be implemented. They will not be reported as tests of our hypotheses and thus will not inflate Type 1 error. We will engage in the following practices: 1) We will report any fatalities as they occur, as required by the university IRB. 2) Our statistician will conduct interim analyses at months 18 and 27 after the start of the study (9 and 18 months after recruiting begins), examining our primary outcome of substance use days in the two arms. She will share the results with UW's independent Data Safety and Monitoring Board but not with the Pls unless instructed to do so by the Board. Because all of our prior research has been designated low-risk by

the IRB, we anticipate the same designation in this case. Barring exceptional disparities in outcomes between conditions, we do not anticipate stopping the trial. As an *a priori* rule, we believe we should stop if our primary outcome of functional health shows a T-score difference greater than 6 (averaged across components of the PROMIS-29). A T-score of 6 is at the very upper end of the clinically meaningful differences for PROMIS-29 components (e.g. physical function, pain, fatigue).^{22,30} We have no reason to anticipate such an occurrence. We will follow Data Safety Monitoring Board guidance on this matter.

Missing Data. In previous RCTs, we completed about 85% of interviews through 12 months and kept missing data on core interview items to about 2%. We expect these rates in this study. We will identify missing data patterns and use pattern-mixture modeling to test the sensitivity of our analysis to missing data assumptions.¹⁰³⁻¹⁰⁶ We will conduct other sensitivity analyses after imputing missing data with a range of plausible values based on assumptions for the missing data (e.g. best-case, worst-case; with and without multiple imputation).¹⁰⁷⁻¹⁰⁹

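### The interim looks do not compute the statistic that the stopping rule uses, and the claim of no Type 1 inflation does not follow

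*Combined protocol and SAP*

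**What the plan says.** All of this is in section 8.0, Interim Analyses and Stopping Plan, unless noted.

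- **Purpose of the looks:** "The interim analyses are solely to check whether the stopping plan needs to be implemented".
- **Content of the looks:** the statistician is described as "examining our primary outcome of substance use days in the two arms".
- **Rule:** the investigators would "stop if our primary outcome of functional health shows a T-score difference greater than 6 (averaged across components of the PROMIS-29".
- **Error control:** "They will not be reported as tests of our hypotheses and thus will not inflate Type 1 error". No alpha, boundary or adjustment is given.
- **Authority:** "We will follow Data Safety Monitoring Board guidance on this matter".
- **Timing:** "interim analyses at months 18 and 27 after the start of the study (9 and 18 months after recruiting begins".
- **Design (section 7.0):** "198 dyads will be recruited, 66 in each of 3 conditions to yield approximately 180 dyads at 8-month analysis".

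Sections 2.0 (Aim 2) and 5.0 (Study design and outcomes) list two primary outcomes, drinker percent heavy drinking days and dyad quality of life. Drinker percent days of alcohol or drug use is secondary outcome 6. Table 2 in section 6.0 gives PROMIS 29.2 as the quality-of-life measure.

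**The concern.** A look that exists only to check a rule should produce the number that the rule needs. Here the look is on drinking or drug use, the rule is on a health-status score, and the look covers one arm fewer than the trial has. A statistician following the paragraph literally would send the board an analysis that cannot be held against the threshold. One who tried to apply the threshold would have to choose the arms, the visit, whose scores to use and the direction. Two competent statisticians could therefore report different statistics.

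The Type 1 sentence adds a separate problem. Whether a look inflates error depends on whether it can end the trial and on what is then tested. Leaving the look out of the report changes neither.

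**Working it through.** **Step 1. The look, the rule and the trial side by side.**

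| Item | Interim look | Stopping rule | Trial as defined elsewhere |
|---|---|---|---|
| Outcome | Substance use days, called primary | Functional health, called primary; PROMIS-29 average | Primaries: heavy drinking days; quality of life (PROMIS 29.2). Use days: secondary |
| Arms | Two | Not stated | Three, 66 dyads each |
| Visit | Not stated | Not stated | 0, 4, 8, 12 months |
| Whose score | Not stated | Not stated | Both dyad members for quality of life |
| Direction | Not stated | Not stated | Favourable direction set by Hypothesis 1 |

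Substance use days may mean secondary outcome 6, or loosely heavy drinking days. Neither is a PROMIS-29 score, so the mismatch does not depend on which was meant. The components that the plan names include physical function, pain and fatigue. If each is scored in the direction of its name, a plain average mixes scores where higher is better with scores where higher is worse.

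The plan gives no error rate for the looks, so there is no figure to reproduce. Steps 2 to 4 show how much the open choices matter.

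**Step 2. Dyads per arm at the first look (month 18).** Per arm = rate × (18 − start − visit) / 3, with 14 to 20 dyads a month (section 4.0), equal arms and no attrition. The look times imply a start at 18 − 9 = 27 − 18 = month 9. Section 5.0 gives Aim 1 as Months 1–6 and the RCT as Months 7–30, which implies 6 elapsed months.

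- Month-8 data, start 9: 14 × 1 / 3 = 4.7 to 20 × 1 / 3 = 6.7, so 5 to 7.
- Month-8 data, start 6: 14 × 4 / 3 = 18.7 to 20 × 4 / 3 = 26.7, so 19 to 27.
- Month-4 data, start 9: 14 × 5 / 3 = 23.3 to 20 × 5 / 3 = 33.3, so 23 to 33.

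**Step 3. Chance of crossing with no true effect.** For any of three pairs this is the chance that the range of three means exceeds 6: 1 − ∫ 3φ(x)[Φ(x + w) − Φ(x)]² dx, with w = 6√n / SD. The documents give no SD, so 5 to 10 is assumed.

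| n per arm | SD 5 | SD 7 | SD 10 |
|---|---|---|---|
| 5 | 13.9% | 36.5% | 60.9% |
| 7 | 6.4% | 24.4% | 50.0% |
| 19 | 0.1% | 2.25% | 15.4% |
| 27 | <0.1% | 0.5% | 7.0% |
| 23 | <0.1% | 1.0% | 10.4% |
| 33 | <0.1% | 0.1% | 3.9% |

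**Step 4. Type 1 error for one pair on the PROMIS outcome.** Simulation with 2,000,000 draws: stop if the absolute difference exceeds 6 at either look and test the data in hand at two-sided 5% (assumed). Otherwise test at 180 / 3 = 60 per arm. Second-look numbers use month 27 in the step 2 formula, capped at twelve months' accrual (14 × 12 / 3 = 56) and at 60.

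| Looks at n per arm | SD 5 | SD 7 | SD 10 |
|---|---|---|---|
| 5, 47 (month 8, start 9) | 9.5% | 8.7% | 7.9% |
| 7, 60 (month 8, start 9) | 7.2% | 9.0% | 8.1% |
| 19, 56 (month 8, start 6) | 5.0% | 5.5% | 8.7% |
| 27, 60 (month 8, start 6) | 5.0% | 5.1% | 6.7% |
| 23, 56 (month 4, start 9) | 5.0% | 5.2% | 8.0% |
| 33, 60 (month 4, start 9) | 5.0% | 5.0% | 5.7% |

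If the stop is for harm only, false claims of benefit are 2.4 to 2.5% against a nominal 2.5%.

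**Step 5. Calendar (minor).** Start 9 + 12 months of accrual + 12 months of follow-up = month 33, beyond Months 7–30. Start 6 gives 6 + 12 + 12 = 30, which fits.

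**The case against.** The rule is advisory, the board decides, and section 10.0 allows the monitoring committee an interim analysis beyond its standard reports. That stands, and it limits the harm. It does not cure the mismatch, because section 10.0 names no outcome, arms or visit either, and the board still needs the right statistic.

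Three stronger readings are tempting, and the documents do not support them.

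- **That the plan inflates Type 1 error, or would often stop by chance.** The 61% corner needs month-8 data only, the slowest accrual, the largest assumed SD, a month-9 start and any of three pairs. At 5 per arm, SD alone moves the figure from 14% to 61%. Counting every crossing as a false finding takes one-pair error up to 37%, but the plan never treats a crossing as an efficacy claim. If the final test is on heavy drinking days, the outcome used to power the study, error is 5.0% at zero correlation with the PROMIS score, at most 5.4% at 0.3 and at most 6.2% at 0.5 (correlations assumed).
- **That heavy drinking days is left out of monitoring.** The label substance use days is called primary and may be a loose name for it. The text is ambiguous.
- **That the analysis was planned for two arms.** Section 8.0 also says "We will report descriptive statistics for all demographic and clinical variables in both arms", but this concerns baseline descriptives, and the same section names all three arms in the outcome model. It is a clerical slip.

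**Conclusion.** The point holds as a contradiction in the text, and that part needs no assumption. The look described is not the analysis that the stopping rule requires, its arm count conflicts with the design, and the rule is not fully defined. The inference from not reporting a look to not inflating Type 1 error is invalid.

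The size of any inflation is none to modest: about 5 to 9% for one pair, only with a binding two-directional stop and an unadjusted test on the PROMIS outcome, and none for a harm-only rule. The null crossing chance at the first look is about 6 to 61%, 0 to 15% or 0 to 10% in the three scenarios of step 2. These figures rest on an assumed SD of 5 to 10, forecast accrual and no attrition. They illustrate what the plan leaves open and do not predict the trial's behaviour. This should be fixed. Confidence is high for the textual mismatch and lower for the magnitudes.

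**What to change.** Reconcile the interim paragraph of section 8.0:

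- Have the interim analysis compute the same outcome that the stopping rule uses, named as in the trial's outcome list, across all three arms.
- State the arm contrast, visit, direction and how the two dyad members' scores are combined, and confirm that component scores point the same way before averaging.
- Replace the Type 1 sentence with either a statement that the looks are for harm only with no efficacy claim, or a stated alpha-spending boundary.
- Reconcile the look calendar with Months 7–30, and correct the arm count in the baseline descriptives sentence.

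The threshold and the choice of stopping criterion stay with the sponsor and the board. The cost is protocol and SAP wording only, with no new data and no extra staff.
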